## Schedule of Assessments

Measures and Data Collection Timeline	Baseline Hospital	SNF Discharge	Post SNF Discharge	
			7-Days	90- Days
Descriptives			Telephone Interviews	
Demographics and Length of Stay	X	X		
Elixhauser Comorbidity Index	X			
Patient Attitudes Toward Deprescribing (PATD)*	X			X
Primary Outcome – Medications				
Total number and type of Routine and PRN Medications, including PIMs	X	X	X	X
Pharmacy Calls to Verify Refill History	X			X
Drug Burden Index (DBI)	X	X		X
Medication Adherence (ARMS)*	X		X	X
Secondary Outcome – Geriatric Syndromes				
Cognitive Impairment (BIMS)*	X		X	X
Delirium (BCAM)*	X		N/A	N/A
Depression (PHQ-9)*	X		X	X
Urinary Incontinence (ICIQ-UI SF)*	X		X	X
Unintentional Weight Loss (DETERMINE)*	X		X	X
Pain (Brief Pain Inventory, BPI-short form)*	X		X	X
Falls	X		X	X
Pressure Ulcers	X		X	X
Secondary Outcome – Health Status				
Functional Health Status (VES-13)*	X		X	X
Secondary Outcomes – Safety				
Unplanned Healthcare Utilization (hospitalizations, emergency room visits)		X	X	X
Adverse Drug / Withdrawal Events	X	X	X	X
Status: Long-Term Care, Hospice, Death		X	X	X
Implementation Evaluation				

Veteran & Provider Barriers and Facilitators	X		X	X
System-Level Factors related to Sustainability		X	X	X
Staff Time for Intervention Implementation	X	X	X	X
Stakeholder Input	X			

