### Outcomes

**Hypotheses 1a -1b:** Among participants assigned to the intervention group, we will summarize both the number of deprescribing *recommendations* and the number of actual medication *changes* at hospital and SNF discharge and 90-days following SNF discharge. The effect of the intervention on the total number of medications, PIMs, and medications associated with geriatric syndromes at hospital discharge, SNF discharge, and 90-days following SNF discharge will be assessed using mixed effects Poisson regression, allowing for overdispersion (more or less variability than is expected under the Poisson regression model), and adjusting for measurement time point (as a categorical covariate) and the total number of medications at enrollment and the interaction of intervention and time point. The heterogeneity in outcome measures across participants will be modeled using a random intercept term, indexed by subject. Heterogeneity among VA providers and SNFs in the effectiveness of intervention will be modeled using a random intervention effect, indexed by VA provider and SNF. The overall intervention effect will be evaluated using a Wald-type multiple degree-of-freedom test against the null hypothesis of no effect at any time point. The intervention effect at each time point will be summarized using a Wald-type 95% confidence interval. Model fit will be assessed by examining the associated Pearson residuals and other graphical methods. Alternative regression techniques may be used in the case of poor fit, for example, negative-binomial regression. A secondary analysis to explore the possibility of intervention effect modification by hospital length of stay (e.g., longer stay may result in more deprescribing) will be implemented by considering the interaction of hospital length of stay with intervention.

**Hypothesis 1c:** The effect of intervention on the anticholinergic and sedative drug burden index scores at hospital discharge, SNF discharge, and 90-days following SNF discharge will be assessed using linear mixed effects

regression, adjusting for measurement time point, its interaction with intervention and using random effects, testing and summary methods as described for Hypotheses 1a, 1b and 1d. Model fit will be assessed using residual diagnostics and graphical methods. Due to the constrained nature of the DBI values, a ‘beta’ regression method may be required, which is suitable for scores that often occur at a boundary.

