**Hypothesis 2a:** Medication adherence will be measured using the ARMS based on an ordinal scale. Functional health status will be measured using the VES-13 total score, also an ordinal outcome. Patient attitudes toward deprescribing (PATD) also will be measured on an ordinal scale. The effects of intervention on these outcomes will be assessed at 7 (except PATD) and 90-days following SNF discharge using mixed-effects logistic regression or proportional odds logistic regression similar to analyses for Hypothesis 2b.

**Hypothesis 2b:** The prevalence and severity of geriatric syndromes will be analyzed at baseline, 7 and 90 days following SNF discharge. The effects of intervention on the prevalence of each type of geriatric syndrome will be assessed using mixed-effects logistic regression, adjusting for measurement time point (categorical) and its interaction with intervention. The severity of each geriatric syndrome is measured on an ordinal scale. Thus, severity will be analyzed using mixed-effects proportional odds logistic regression, also adjusting for measurement time point and its interaction with intervention. For either method random effects, testing, summary and diagnostic methods will be used as described for Hypotheses 1a, 1b and 1d.

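### Hypothesis 2a names no baseline-score covariate for ARMS, VES-13 or PATD, although all three are collected at baseline; neither reading of the text gives baseline adjustment, which costs precision on secondary outcomes

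*Combined protocol and SAP*

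**What the plan says.** Under Statistical Considerations, Outcomes, Hypothesis 2a, the plan says of ARMS, VES-13 and PATD: "The effects of intervention on these outcomes will be assessed at 7 (except PATD) and 90-days following SNF discharge using mixed-effects logistic regression". The sentence then allows a proportional odds model as an alternative and likens the analyses to those of Hypothesis 2b. The time points named are therefore 7 and 90 days, and 90 days only for PATD. No baseline covariate is mentioned.

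The Hypothesis 2b paragraph, to which 2a refers, does include baseline, but as a time point: "The prevalence and severity of geriatric syndromes will be analyzed at baseline, 7 and 90 days following SNF discharge". Its model terms are time point and its interaction with intervention: "severity will be analyzed using mixed-effects proportional odds logistic regression, also adjusting for measurement time point and its interaction with intervention". It names no baseline-score covariate either. It takes its random effects from the Hypothesis 1 models, where heterogeneity between participants is "modeled using a random intercept term, indexed by subject".

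Three other places bear on the point:
- The Schedule of Assessments collects ARMS and VES-13 at baseline, 7 days and 90 days, and PATD at baseline and 90 days.
- The Hypotheses 1a-1b models adjust for the number of medications at enrollment, so the plan uses baseline adjustment elsewhere.
- Repeated Measures provides a fallback, with robust standard errors, if a mixed model cannot be implemented. It does not say which method would be used.

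**The concern.** Hypothesis 2a is framed as an improvement in adherence and health status, and each Veteran's starting score on the same scale is already scheduled. Adjusting for that score is the usual way to gain precision in a randomized comparison at no cost in data. The 2a paragraph does not say that it will be done.

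At stake is power on outcomes with substantial attrition by 90 days. The text also allows analysts to fit materially different models from one sentence. PATD raises a further question: if only its 90-day value is an outcome, a subject random intercept has one observation per Veteran to work with.

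**Working it through.** **1. The plan's own figure.** Sample Size and Randomization states more than 93% power for 260 Veterans. It gives no effect size, SD, event rate, alpha or correlation, so the figure cannot be reproduced. Assuming a two-sided 0.05 test and 1:1 allocation, the standardized difference detectable with 93% power is (1.960 + 1.476) × √(2/n per arm):
- all 260 analysed (130 per arm): 0.43 SD
- 85 per arm: 0.53 SD
- 94 per arm: 0.50 SD

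**2. The 90-day sample.** The plan ends at 354 of 540, or 65.6%. Applied to 260 this gives 170, or 85 per arm. Its stated rates, each applied once, give 260 × 0.95 × 0.85 × 0.90 = 189, or about 94 per arm. The two differ because 85% of 513 is 436, not 393; the plan's 393 already contains a 10% loss, and 354 takes 10% off again. The choice does not affect step 3, because that formula starts from a power and contains no n.

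**3. Follow-up only, without and with the baseline covariate.** With correlation ρ between baseline and follow-up score, adjustment multiplies the residual variance by 1 − ρ². Then

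adjusted power = Φ[(1.96 + z_power)/√(1 − ρ²) − 1.96].

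Example, 80% and ρ = 0.5: (1.96 + 0.842)/0.866 − 1.96 = 1.275, and Φ(1.275) = 0.899.

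| Assumed ρ | 1 − ρ² | From 80% | From 93% |
|---|---|---|---|
| 0.3 | 0.91 | 83.6% | 95.0% |
| 0.5 | 0.75 | 89.9% | 97.8% |
| 0.6 | 0.64 | 93.8% | 99.0% |

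This is a normal approximation for a single 90-day comparison. It ignores provider and SNF clustering and the joint test over time points.

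**4. Check with ordinal models.** Proportional odds models were simulated with an 8-level score, 85 per arm, a latent effect of 0.43 SD and 400 runs per setting. Power without and with baseline was 75% and 79% at ρ = 0.3, 80% and 89% at 0.5, and 75% and 96% at 0.7. The unadjusted figures differ only by simulation error, about √(0.8 × 0.2/400) = 2 percentage points. The approximation in step 3 is adequate.

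**5. Baseline as an outcome time point, as in 2b.** With a free time-by-intervention interaction, each arm has its own mean at baseline and at each follow-up. The group contrast at follow-up then gains essentially no precision from the baseline rows. If the effect is instead read as change from baseline, the variance factor is 2(1 − ρ). From an 80% reference, power is 66% at ρ = 0.3, 80% at 0.5 and 95% at 0.7, against 83.6%, 89.9% and 97.5% with the baseline covariate. Below ρ = 0.5, change from baseline does worse than follow-up alone.

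**6. PATD with one outcome value.** In one simulated ordinal data set with a single value per subject, the random-intercept SD was varied from 0 to 4. The log-likelihood moved only from −268.72 to −268.62, while the intervention log-odds ratio moved from 0.30 to 0.85. The intercept variance is practically unidentified, yet the effect estimate depends on it.

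**The case against.** Several stronger readings are tempting, and the documents do not support them.

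- *The 2a models use only follow-up values.* The time points named in 2a suggest this, but the same sentence calls the analyses similar to 2b, and 2b includes baseline. The text is ambiguous.
- *The PATD model is unidentifiable as specified.* This requires 2b's random effects to carry into 2a but not its baseline time point. If 2b carries over in full, PATD has two values per Veteran. The 2a wording also offers proportional odds regression without repeating that it is mixed-effects, and Repeated Measures has its fallback. A sound model is permitted, though not prespecified.
- *The effect estimates would be biased.* Allocation is randomized 1:1. Omitting baseline widens the intervals and does not bias the comparison.
- *A primary outcome is affected.* The schedule lists ARMS under the primary-outcome heading, but Study Design and Description of Assessments both place adherence among the secondary outcomes. PATD is listed with the descriptives and is not part of Hypothesis 2a as worded in Overview and Objectives.

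The best remaining objection concerns size. Baseline is measured during an acute hospital stay, and the Background says syndromes develop or worsen in that period, so a high correlation with later scores cannot be presumed. At 0.3 the gain is about 4 points from 80% and 2 points from 93%. That stands, and it makes the size uncertain. It does not remove the case for adjustment, since the stated 93% cannot be verified and the covariate requires no new data.

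**Conclusion.** The point holds as one of omission and ambiguity. No baseline-score covariate is named for 2a, or for the 2b model it cites, and neither reading of the cross-reference provides baseline adjustment. The consequence is avoidable loss of precision on secondary outcomes.

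The size rests on a correlation that the documents do not give. Over assumed values of 0.3 to 0.6, adjustment would add about 4 to 14 percentage points to a power of 80%, or 2 to 6 points to the stated 93%. A gain of 5 points or more needs a correlation of about 0.5 or above and, at 0.5, power below the stated 93%, where the gain is 4.8 points. The PATD random-intercept problem is conditional on how the cross-reference is read, and is best closed by explicit wording.

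**What to change.** In Outcomes, Hypothesis 2a, replace the cross-reference with explicit models:

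- **ARMS and VES-13:** the 7- and 90-day values are the outcomes, and the Veteran's own baseline score on the same scale is a covariate. Baseline is not also an outcome row.
- **PATD:** a single-time-point proportional odds model at 90 days with baseline PATD as a covariate and no subject random intercept. Name the item or score analysed, because Description of Assessments lists ten Likert items and five further questions but defines no total.
- **Missing baseline scores:** mean imputation with a missing indicator, so that no Veteran is dropped for lack of a baseline. Such gaps are likely, because Study Procedures does not include ARMS or VES-13 among the assessments a surrogate can complete.

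The cost is SAP wording only, since the scores are already scheduled. The downside is that the odds ratios become conditional on the baseline score, which the report should state.

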**Hypothesis 1d:** DROP will result in significantly fewer medications associated with geriatric syndromes at hospital discharge, SNF discharge and 90-days after SNF discharge.

**Specific Aim 2:** Document the effects of a Veteran-centered deprescribing intervention (DROP) on medication adherence, health status, and geriatric syndromes.

**Hypothesis 2a:** DROP will result in a significant improvement in medication adherence and self-rated health status at 7 and 90 days after SNF discharge.

**Hypothesis 2b:** DROP will result in a lower prevalence and severity of geriatric syndromes at 7 and 90 days after SNF discharge.

**Specific Aim 3:** Evaluate intervention implementation to inform future adoption and sustainability.

**Aim 3a:** Identify patient-level barriers and facilitators of DROP.

[figure not shown]
**Aim 3b:** Identify VA and Non-VA provider-level barriers and facilitators of DROP.

**Aim 3c:** Identify system-level factors that influence sustainability after hospital discharge.

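### Read as written, the Hypothesis 2b test counts the pre-intervention baseline difference as an intervention contrast, and the 7- and 90-day syndrome effects are not baseline-adjusted

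*Combined protocol and SAP*

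**What the plan says.** Under Statistical Considerations, Outcomes, the Hypothesis 2b paragraph opens: "The prevalence and severity of geriatric syndromes will be analyzed at baseline, 7 and 90 days following SNF discharge". Prevalence of each syndrome is modelled by "mixed-effects logistic regression, adjusting for measurement time point (categorical) and its interaction with intervention", and severity by "mixed-effects proportional odds logistic regression, also adjusting for measurement time point and its interaction with intervention". No baseline syndrome value is named as a covariate. The paragraph ends: "For either method random effects, testing, summary and diagnostic methods will be used as described for Hypotheses 1a, 1b and 1d".

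The Hypothesis 1 paragraph of the same section defines what is borrowed: "The overall intervention effect will be evaluated using a Wald-type multiple degree-of-freedom test against the null hypothesis of no effect at any time point". It adds: "The intervention effect at each time point will be summarized using a Wald-type 95% confidence interval". There, the time points are hospital discharge, SNF discharge and 90 days after SNF discharge, and the count models adjust for the number of medications at enrollment.

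The Précis states Hypothesis 2b more narrowly: "DROP will result in a lower prevalence and severity of geriatric syndromes at 7 and 90 days after SNF discharge".

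The Pre-Review section places the medication review after the baseline assessments. The Description of Assessments says that the delirium screen is not repeated after the hospital stay, because it cannot be done by telephone.

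**The concern.** In Hypothesis 1 every analysed time point is an outcome time point, so a joint test over all of them tests the intervention. Hypothesis 2b takes over that test but changes the time points, and one of them is now baseline. An arm difference there cannot be an effect of DROP. Nothing in the text sets it to zero, leaves it out of the joint test, or uses the baseline value as a covariate.

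Three things are at stake:
- A rejection for a syndrome may come from imbalance at enrollment and yet be reported as an effect on health outcomes.
- A degree of freedom goes to a contrast that carries no information about the hypothesis.
- The 7- and 90-day estimates carry any baseline imbalance forward and are less precise than the collected data allow.

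**Working it through.** **The plan's own figure.** The only stated figure that covers 2b is power above 93% with 260 Veterans. It cannot be reproduced, because no effect size, SD, prevalence, alpha or correlation is given. The checks below assume two-sided 5%.

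**Step 1: which contrasts are tested.** Baseline, day 7 and day 90, categorical time, an interaction with intervention and no constraint give three arm contrasts. The test of no effect at any time point is then on 3 df (critical value 7.81). The hypothesis in the Précis needs 2 df (5.99).

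**Step 2: what baseline contributes.** In large samples the joint statistic splits as Q(3 df) = z₀² + Q(2 df, given baseline), where z₀ is the baseline z-value and the parts are independent. With no true effect,

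P(reject | z₀) = exp(−(7.815 − z₀²)/2), or 1 once z₀² exceeds 7.815, that is |z₀| ≥ 2.80.

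| baseline \|z₀\| | 0 | 1 | 1.5 | 1.96 | 2.5 | ≥ 2.80 |
|---|---|---|---|---|---|---|
| P(reject) | 2.0% | 3.3% | 6.2% | 13.7% | 45.7% | 100% |

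Averaged over z₀ this is 5%. About 39% of these false rejections would not be significant on the 2-df baseline-adjusted test. The schedule lists eight syndromes. If they are treated as independent (an assumption), the chance that at least one has baseline |z| > 1.96 is 1 − 0.95⁸ = 34%.

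A null simulation gives the same picture: 1,000 trials of 260, a binary outcome, and logistic GEE standing in for the mixed model, with assumed random-intercept SD 1.5 and intercept −1. Overall rejection was 4.4% (3 df) and 4.7% (common baseline, 2 df). Among the 106 trials with baseline |z| > 1.645, it was 16.0% and 1.9%.

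**Step 3: power and precision.** Numbers per arm, from the plan's attrition rates applied to 130:
- Day 7: 130 × 0.95 × 0.90 = 111, assuming that the 10% not reached also applies at day 7.
- Day 90: 130 × 0.95 × 0.85 × 0.90 = 94.

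Further assumptions are unit SD, a Gaussian outcome, exchangeable correlation ρ, monotone dropout and a 0.3 SD effect at both follow-ups. Variances come from the generalised least squares information matrix, summed over the dropout patterns. With complete data, the variance ratio of the unconstrained to the common-baseline model is 1/(1 − ρ²), which is 1.04 at ρ = 0.2 and 1.96 at 0.7. With dropout:

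| ρ | variance ratio, day 7 | variance ratio, day 90 | power, 3 df | power, 2 df |
|---|---|---|---|---|
| 0.2 | 1.04 | 1.03 | 67.5% | 73.7% |
| 0.3 | 1.08 | 1.07 | 67.8% | 74.0% |
| 0.4 | 1.16 | 1.14 | 69.7% | 75.8% |
| 0.5 | 1.28 | 1.25 | 73.6% | 79.3% |
| 0.6 | 1.48 | 1.42 | 79.6% | 84.6% |
| 0.7 | 1.82 | 1.71 | 87.8% | 91.3% |

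The two tests have the same noncentrality (9.48 for both at ρ = 0.5). The loss of about 4 to 6 points therefore comes only from the extra degree of freedom. Where the 2-df test has 93% power, the 3-df test has 89.9%.

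**Step 4: delirium.** With no day-7 or day-90 value, the only intervention contrast that can be estimated is the one at baseline.

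**The case against.** **The reading is not forced.** The sentence listing baseline may be descriptive, and the sentence on intervention effects names no times. An analyst might test only the two interaction terms, that is, change from baseline, and the problem would then largely disappear (simulated size 5.2%). This is a fair point, and it is why the finding is stated for the text as written. But the plan says neither of these things, and "Wald-type multiple degree-of-freedom test against the null hypothesis of no effect at any time point" with an interval at each time point favours the literal reading. Under either intention the wording needs correcting.

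**Error control is intact.** This stands. A reader might infer from the 14% and 46% figures that the test is anti-conservative. It is not: those figures condition on uncommon imbalances and are offset by 2% when the arms are balanced. Time-specific intervals and a baseline-balance summary are also planned, so a baseline-driven rejection could be spotted.

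**Baseline information is not wholly lost.** This also stands. The joint test already uses it, as the equal noncentralities show. Nor are the follow-up estimates simply raw differences: with dropout, the mixed model recovers about 4 to 11% of the raw variance at ρ = 0.5 to 0.6.

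**Hypothesis 2a.** A reader might extend the 3-df criticism to ARMS, VES-13 and PATD, because they are analysed in a similar way to 2b. The text limits 2a effects to 7 days (except PATD) and 90 days, so only the missing baseline adjustment applies there.

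**The baseline contrast may not be exactly zero.** The analysis set is restricted to Veterans discharged to SNF, which is decided after randomization, and baseline interviews of delirious Veterans may be delayed. This limits when a common baseline mean can be imposed.

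**Conclusion.** The concern holds for the plan as written, as a mismatch between test and hypothesis and a loss of efficiency. It is not an inflation of type I error. A rejection on 2b can be produced by chance imbalance before the intervention. The conditional probabilities rest only on large-sample theory and a 5% level.

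The power cost (about 4 to 6 points) and the variance ratios (about 1.03 to 1.82) rest on the assumed correlation of 0.2 to 0.7, the 0.3 SD effect, 130/111/94 per arm and a Gaussian approximation. They do not transfer directly to logistic or proportional-odds mixed models.

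A reader might conclude that this undermines the trial's main result. The documents do not support that: the syndromes are secondary outcomes, and the Hypothesis 1 medication analyses do not list baseline as a time point. It should be fixed, but it is not disqualifying.

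**What to change.** In the Hypothesis 2b paragraph:
- State that the intervention effect is tested at 7 and 90 days only, by a 2-df Wald test, with intervals at those two times.
- Include the baseline value of the same syndrome as a covariate. Alternatively, keep baseline as an outcome row with one mean common to both arms, but only if baseline is measured before any intervention contact and in all randomized Veterans.
- Say how assessments delayed by delirium are classified, and how missing baseline values are handled.
- Report delirium descriptively, with no intervention test.

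For Hypothesis 2a, keep the stated time points and add the collected baseline ARMS, VES-13 or PATD value as a covariate.

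The cost is a few sentences and one model statement. All the baseline measures are already in the Schedule of Assessments, so no new data are needed.
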